*** Purpose, Study Procedures, Background ***

Original Protocol Number (e.g., 07-226H)

Cloned and subsequently modified from 14-5531H

Title (Please indicate if the protocol title is different from the proposal title)

Does Dapagliflozin Provide Additional Health Benefits To Dietary Counseling For Weight Loss?
Clinical Research Protocol Title: Dapagliflozin Promotes Favorable Health Benefits That Are Independent Of Weight Loss In Overweight/Obese Adults

Complete Sections 1 - 16. Specify N/A as appropriate. Do not leave any required sections blank.

1. Purpose of the study

a) Provide a brief lay summary of the project in <200 words. The lay summary should be readily understandable to the general public, and is, for example, what would be released to a newspaper if requested.

THIS PROTOCOL IS AN AMENDED/SIMPLIFIED VERSION OF IRB PROTOCOL 14-5531H.

Dapagliflozin is a medicine to treat diabetes. Its mechanism of action is via sodium-glucose co-transporter 2 (SGLT2) inhibition. In adults with diabetes, use of sodium-glucose co-transporter 2 inhibitors is associated with moderate weight (fat) loss, in addition to other health benefits, including decreased blood pressure, decreased inflammation, and decreased oxidative stress. It is unclear as to whether these health

Protocol Title: Does Dapagliflozin Provide Additional Health Benefits To Dietary Counseling For Weight Loss?
Clinical Research Protocol Title: Dapagliflozin Promotes Favorable Health Benefits That Are Independent Of Weight Loss In Overweight/Obese Adults

Protocol Type: Biomedical

Date Submitted: 03/01/2018

Approval Period: Draft

Important Note: This Print View may not reflect all comments and contingencies for approval. Please check the comments section of the online protocol.
Questions that appear to not have been answered may not have been required for this submission.
Please see the system application for more details.

benefits are due to SGLT2 inhibition per se, or as a secondary effect of weight loss. We wish to compare the health benefits of dietary counseling for weight loss with and without concomitant use of an SGLT2 inhibitor.

b) What does the Investigator(s) hope to learn from the study?

We wish to learn if:

1. Dapagliflozin (SGLT2 inhibition) provides additional health benefits to dietary counseling for weight loss?

and if,

2. Weight loss associated with dietary counseling and the use of Dapagliflozin (SGLT2 inhibition) is characterized by normal circulating satiety signals rather than the usual diet-induced changes in circulating peptides that increase hunger and reduce satiety.

c) Proposed Start Date (may not precede IRB approval date):

On receipt of IRB approval.

2.

Study Procedures (If this is a student project, the methods section of the thesis or dissertation proposal must be attached in section #16 - Attachment section.)

a) In lay language, describe all the procedures, from screening through end-of-study, that the human subject must undergo in the research project, including study visits, drug treatments, randomization and the procedures that are part of standard of care. Please note: Do NOT respond "See Attachment Section." If you would like to add tables, charts, etc., attach those files in the Attachment section (#16).

OVERVIEW

This is a randomized, prospective, placebo-controlled, double blind, repeated measures study. 60 overweight/obese adults (body mass index > 27.5 kg/m²) will be recruited for participation and randomly assigned to one of two 12 week treatments: (1) daily oral administration of Dapagliflozin with dietary counseling to promote weight loss; or, (2) daily oral administration of a placebo with dietary counseling to promote weight loss.

Study participants will report to the research facilities on the Colorado State University main campus on 29 separate occasions:

Visit 1: study participants will undergo screening: medical history, 12-lead electrocardiogram and blood pressure assessment at rest and during incremental exercise to volitional exhaustion, blood sampling, and measurement of body composition.

Visit 2: an oral glucose tolerance test will be performed and resting metabolic rate and blood pressure will

Protocol Title: Does Dapagliflozin Provide Additional Health Benefits To Dietary Counseling For Weight Loss?
Clinical Research Protocol Title: Dapagliflozin Promotes Favorable Health Benefits That Are Independent Of Weight Loss In Overweight/Obese Adults

Protocol Type: Biomedical

Date Submitted: 03/01/2018

Approval Period: Draft

Important Note: This Print View may not reflect all comments and contingencies for approval. Please check the comments section of the online protocol.
Questions that appear to not have been answered may not have been required for this submission.
Please see the system application for more details.

be measured.

Visit 3: appetite and hunger will be assessed and participants will be given a 3-dietary record form to complete.

Visits 4-27: 12 weeks of nutrition counseling/weighing (upto 2 visits per week for 12 weeks). Concurrent with these visits, research participants will ingest, on a daily basis, either Dapagliflozin or placebo.

Visit 28: an oral glucose tolerance test will be performed and resting metabolic rate and blood pressure will be measured.

Visit 29: appetite and hunger will be assessed; body composition will be measured, and participants will be given a 3-day dietary record form to complete.

DETAILED DESCRIPTION OF STUDY PROCEDURES

Visit 1: study participants will provide informed consent and undergo screening: medical history, 12-lead electrocardiogram and blood pressure assessment at rest and during incremental exercise to volitional exhaustion, blood sampling, and measurement of body composition.

These screening procedures are standard for our lab. Each of the procedures is currently active in other IRB-approved protocols (e.g. 12-3767H, 08-611H, 14-4756H).

Health History - Potential participants will complete a standardized health history questionnaire that will address past and present medication use, allergies, past and present medical conditions and physical injuries, and habitual use of alcohol and tobacco.

Body composition - Percent body-fat, fat-free mass, total and regional adipose tissue mass, and total bone mineral density will be determined using a whole-body dual energy x-ray absorptiometry scan (DEXA, Model DPX-IQ Lunar Corp., Madison, WI).

Maximal graded exercise stress testing - A 12-lead ECG, arterial blood pressure (brachial sphygmomanometer) will be obtained during quiet resting conditions in the supine and upright sitting positions, and during incremental stationary cycle ergometer or treadmill exercise until volitional fatigue. During exercise, oxygen consumption, carbon dioxide production and ventilation may be determined by indirect calorimetry. All data from these tests will be reviewed by a cardiologist. Only those subjects demonstrating no signs or symptoms of disease will be invited to participate in the study.

Blood sampling – Blood (~ 20 ml) will be sampled from an antecubital or hand vein for subsequent analysis of circulating factors pertinent to inclusion/exclusion criteria, including glucose, aspartate aminotransferase, alanine aminotransferase, and total bilirubin. These blood analyses will be performed in on-site (Piccolo Xpress, Abaxis, Union City, CA). Testing for Hepatitis B/C will be performed at a local, external clinical lab (e.g. University of Colorado-Health North). Per the Medical Monitor's discretion follow up blood draws maybe requested.

Visit 2: Resting Metabolic Rate (ventilated hood technique, indirect calorimetry) for 45 minutes and blood pressure will be measured. An oral glucose tolerance test will be performed.

Protocol Title:	Does Dapagliflozin Provide Additional Health Benefits To Dietary Counseling For Weight Loss? Clinical Research Protocol Title: Dapagliflozin Promotes Favorable Health Benefits That Are Independent Of Weight Loss In Overweight/Obese Adults
Protocol Type:	Biomedical
Date Submitted:	03/01/2018
Approval Period:	Draft
Important Note:	This Print View may not reflect all comments and contingencies for approval. Please check the comments section of the online protocol. Questions that appear to not have been answered may not have been required for this submission. Please see the system application for more details.

These procedures are standard for our lab. Each of the procedures is currently active in other IRB-approved protocols (e.g. 14-5201H).

Blood pressure will be determined three times using the left arm via standard procedures. Each assessment will be separated by 3 minutes. The mean of the three measurements will be recorded.

Participants will report to the laboratory early in the morning, following a 12-hour fast and 24-hour abstention from exercise. An intravenous catheter will be inserted into an antecubital or hand vein and kept patent with a saline drip. Following baseline blood sampling for fasting glucose and insulin, participants will ingest 75 g of dextrose dissolved in 250 ml of water over 10-minutes. Venous blood (~ 9 ml) will be sampled at time 0 (baseline) and 5, 10, 15, 20, 30, 45, 60, 75, 90 105 and 120 minutes for determination of concentration of blood glucose (2300 STAT Plus Glucose Lactate Analyzer, YSI Inc., Yellow Springs, Ohio), and insulin (commercially available assay).

Prior to the start of the oral glucose tolerance test, venous blood (~ 20 ml) will be sampled, and plasma/serum and red cells isolated and stored at -70°C for subsequent analysis of circulating markers of inflammation (High sensitive C-Reactive Protein, Tumor Necrosis Factor Alpha, and Interleukin 6) and oxidative stress (oxidized low density lipoprotein concentration, and thiobarbituric acid reactive substances).

Visit 3: Appetite and hunger will be assessed.

These procedures are standard for our lab. Each of the procedures is currently active in other IRB-approved protocols (e.g. 12-3567H).

On a day different to the oral glucose tolerance day, participants will report to the laboratory early in the morning, following a 12-hour fast and 24-hour abstention from exercise. An intravenous catheter will be inserted into an antecubital or hand vein and kept patent with a saline drip. Participants will be provided with a standardized "priming meal" comprising a commercially available, mixed-nutrient liquid meal, dosed to 1 kcal per kg body mass (Ensure, Ross Laboratories, Abbott Park, IL; 64% CHO, 22% fat, 14% protein). One hour following consumption of this priming meal, participants will be presented with a pre-weighed buffet of food from which they will have opportunity to eat ad libitum quantities over a 30 minute period. The remaining uneaten food will be reweighed and participants' energy and macronutrient intakes will later be determined using the Food Intake Analysis System software (U Texas Health Sciences Center, Houston). Prior to the standardized primer meal, and to the buffet, and then every 60 minutes over 3 hours following the buffet, participants will be asked to rate their perceptions of hunger and satiety using a visual analog scale. At these same time points, venous blood (~ 20 ml) will be sampled, and plasma/serum isolated and stored at -70°C for subsequent determination of concentrations of hunger and satiety hormones (e.g. ghrelin, peptide YY, leptin, and insulin). At the conclusion of these tests, the study participant will give a form in which to record the amounts of food and beverage (except water) they eat and drink for three consecutive days, including 2 week days and 1 weekend day. Upon completion of the food records, the form will be returned to the research team. This information will be used to establish baseline dietary intake and will be useful information for the nutrition counselors seeking to help the participants lose weight.

Protocol Title: Does Dapagliflozin Provide Additional Health Benefits To Dietary Counseling For Weight Loss?
Clinical Research Protocol Title: Dapagliflozin Promotes Favorable Health Benefits That Are Independent Of Weight Loss In Overweight/Obese Adults

Protocol Type: Biomedical

Date Submitted: 03/01/2018

Approval Period: Draft

Important Note: This Print View may not reflect all comments and contingencies for approval. Please check the comments section of the online protocol.
Questions that appear to not have been answered may not have been required for this submission.
Please see the system application for more details.

Visits 4-27: During the first 6 weeks participants will meet with a study counselor 2 times per week for dietary counseling and measurement of body weight. During the second 6-week period they will meet 1-2 times per week for dietary counseling and body weight measurement, depending on whether or not they are meeting weight loss goals. If they are losing weight as prescribed, they will meet only once per week, but if they are not meeting weight loss goals they will meet 2 times per week. Participants will need to fast for 10 hours prior to the weigh-in. On 2 random counseling occasions between weeks 4 and 10, they will be asked to recall what they ate during the previous 24 hours. If participants fail to achieve their target body weight (within 1 kg or 2.2 lbs) on three consecutive weighing sessions, they will be provided with additional counseling and instructions to aid in achieving your target body weight.

During the first two weeks of the 12 week intervention, participants will ingest one pill daily (5 mg DAPA) and for the remaining 10 weeks participants will ingest 2 pills daily (a total of 10 mg DAPA). On 3 random weigh-in occasions between weeks 4 and 10, participants will be asked to recall what they ate during the previous 24 hours.

Visit 28: Resting Metabolic Rate Test, Oral Glucose Tolerance Test, and Blood Pressure will be measured (e.g. the final week of daily ingestion of Dapagliflozin). See description of Visit 2.

Visit 29: in the HPCRL appetite and hunger will be assessed this visit will occur in week 12 (e.g. during the final week of daily ingestion of Dapagliflozin). Body composition will be measured at this visit or early the following week (e.g. week 13). The study participants will also be given the 3-day food intake record form to be completed and returned to the research team.

b) Explain why human subjects must be used for this project.

Dapagliflozin is approved for human use. Due to potential species differences it would not be appropriate to perform these studies on experimental animals.

c) Alternative Procedures. If the proposed study is a clinical trial of a drug, vaccine, device or treatment, describe alternative procedures, if any, that might be advantageous to the subject. Describe the important potential risks and benefits associated with the alternative procedure(s) or course(s) of treatment. Any standard treatment that is being withheld must be disclosed. This information must be included in the consent form.

There are no appropriate alternative procedures.

d) If the proposed study is a clinical trial of a drug, vaccine, device or treatment, will it be possible to continue the more (most) appropriate therapy for the subject(s) after the conclusion of the study?

Not applicable.

e) Study Endpoint. If the proposed study is a clinical trial of a drug, vaccine, device or treatment, what are the guidelines or end points by which you can evaluate the alternative treatments during the study? If one treatment proves to be clearly more effective than another (or others) will the study be terminated before the projected total subject population has been enrolled? When will the study end if no important

Protocol Title: Does Dapagliflozin Provide Additional Health Benefits To Dietary Counseling For Weight Loss?
Clinical Research Protocol Title: Dapagliflozin Promotes Favorable Health Benefits That Are Independent Of Weight Loss In Overweight/Obese Adults

Protocol Type: Biomedical

Date Submitted: 03/01/2018

Approval Period: Draft

Important Note: This Print View may not reflect all comments and contingencies for approval. Please check the comments section of the online protocol.
Questions that appear to not have been answered may not have been required for this submission.
Please see the system application for more details.

differences are detected?

Not applicable.

f) State if deception will be used. If so, provide a rationale and describe debriefing procedures. Submit a debriefing script in the Attachment Section (#16).

There will be no deception. Subjects may receive Dapagliflozin or a placebo; they will not know which treatment (Dapagliflozin or placebo) they receive until study completion.

3. Background

a) Describe past experimental and/or clinical findings leading to the formulation of the study, if applicable.

Aside from the metabolic benefits pertaining to glucose control, inhibition of sodium-glucose co-transporter 2 (SGLT2) in patients is associated with moderate weight loss (Tahrani et al., 2011; Chen & Leung, 2013), with some studies reporting up to 4.5 kg decreases in body mass over 12 weeks (Wilding et al., 2009). Animal data are consistent with these observations (Devenny et al., 2012; Liang et al., 2012). SGLT2 inhibition is also associated with other health benefits, including decreased blood pressure (Ferrannini et al., 2010; Dobbins et al., 2012), decreased inflammation (Chen et al., 2012; Tahara et al., 2013, 2014), and decreased oxidative stress (Tahara et al., 2013, 2014)—all health benefits with very important implications for improved physiological function and decreased disease-risk. At present, it is unclear as to whether these health benefits are due to SGLT2 inhibition per se, or as a secondary effect of weight loss.

Noteworthy, the weight loss observed in patients associated with SGLT2 inhibition is not mediated by intentional dietary restriction/intervention. It is more likely to be mediated by the caloric loss associated with the decreased renal tubular reabsorption of glucose, leading to urinary glucose excretions ranging between 45 and 80 g/day (180-320 kcal/d), depending on the drug dose (Idris & Donnelly, 2009). This caloric deficit is not trivial. Typically, caloric deficits of this magnitude require either increased physical activity and/or dietary restriction.

In our original study (Protocol 14-5531H) we learned that when adults with normal, healthy glucose control use SGLT2 inhibitors, the weight loss is negligible. Nevertheless, even in healthy adults, SGLT2 inhibition leads to glucose spillage into urine that may elicit other, non-weight loss mediated health benefits. Therefore in the current project we will study the use of SGLT2 inhibitors combined with dietary counseling for weight loss.

The limitations of the use of dietary restriction for weight loss and, perhaps more importantly, sustained lower weight maintenance, are well described (MacLean et al., 2006; Strohacker et al., 2014). In response to diet-induced weight loss several biological factors, including increased appetite owing to elevation of the orexigenic hormone, ghrelin, and decreased anorexigenic hormones like peptide YY (PYY), promote increased dietary intake and subsequently weight re-gain. However, it is biologically plausible that the weight loss accompanying SGLT2 inhibition may not be accompanied by increased appetite as the unique mechanism of action allows the patient to consume/ingest calories (carbohydrates), but limits the ability for internal storage. That is, during eating, nutrient sensors within the gut release satiety factors to inhibit further dietary intake (Schaeffer et al., 2014; Strohacker et al., 2014). Ingesting calories as carbohydrates while using SGLT2 inhibitors may allow for normal satiety signaling while limiting caloric storage, thus thwarting biological impediments to long-term weight loss.

Protocol Title: Does Dapagliflozin Provide Additional Health Benefits To Dietary Counseling For Weight Loss?
Clinical Research Protocol Title: Dapagliflozin Promotes Favorable Health Benefits That Are Independent Of Weight Loss In Overweight/Obese Adults

Protocol Type: Biomedical

Date Submitted: 03/01/2018

Approval Period: Draft

Important Note: This Print View may not reflect all comments and contingencies for approval. Please check the comments section of the online protocol.
Questions that appear to not have been answered may not have been required for this submission.
Please see the system application for more details.

thwarting biological impediments to long-term weight loss.

Accordingly, in light of the rationale provided, we wish to determine if: 1. Dapagliflozin (SGLT2 inhibition) provides additional health benefits to dietary counseling for weight loss? 2. Weight loss associated with dietary counseling and the use of Dapagliflozin (SGLT2 inhibition) is characterized by normal circulating satiety signals rather than the usual diet-induced changes in circulating peptides that increase hunger and reduce satiety.

REFERENCES (Some of which have been provided as attachments)

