Protocol Title: Does Dapagliflozin Provide Additional Health Benefits To Dietary Counseling For Weight Loss?
Clinical Research Protocol Title: Dapagliflozin Promotes Favorable Health Benefits That Are Independent Of Weight Loss In Overweight/Obese Adults

Protocol Type: Biomedical

Date Submitted: 03/01/2018

Approval Period: Draft

Important Note: This Print View may not reflect all comments and contingencies for approval. Please check the comments section of the online protocol.
Questions that appear to not have been answered may not have been required for this submission.
Please see the system application for more details.

* * * Continuing review * * *

To renew your protocol: 1. Complete this one-page form; 2. If necessary, update any sections of the protocol that need to be updated for the upcoming year (e.g., change in personnel, location); 3. Electronically "sign" the application by clicking in the check box on the bottom of the "Obligations" page; 4. Remember to click "Submit Form" and confirm your intent to submit by clicking "OK" so that the IRB administrators receive your application. You must answer each question. Input N/A to answer any questions that are not applicable. NOTE: Documents that contain much of the information required to answer the participant number questions below can be found in the "Event History" section of each protocol. The status on your homepage will be "Submitted to IRB" when your submission is successful. **IMPORTANT:** If the Department Head has changed since your last approval, please be sure to update the Department Head listing on the personnel information screen of your protocol.

1. Summary: Number of Participants Associated with the Protocol:

a. Total number of participants approved to date:

We requested 60 overweight/obese adult volunteers (men and women) will be enrolled. Please see 1.e.

b. Number of participants studied since the last approval date:

80

c. Total number of participants studied since the beginning of the project:

80

d. Number of participants remaining to study (total number of participants approved LESS the total number of participants studied to date):

Please see 1.e.

e. Please explain if there is a discrepancy in participant numbers (e.g., more participants responded to a survey than had been approved):

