Baseline (pre-counselling) differences between placebo and SGLT2 inhibition groups were compared using independent Student t-Tests. Consistent with the experimental design (randomized, double-blind, parallel, repeated measures) the influence of SGLT2 inhibition on the physiological responses to dietary counselling was examined using two-way (group: placebo vs. SGLT2 inhibition x time: before vs. after dietary counselling) analysis of variance (ANOVA). The influence of SGLT2 inhibition and dietary counselling on the dynamic responses to oral glucose ingestion were examined using three-way ANOVA (placebo vs. SGLT2 inhibition x before vs. after dietary counselling x time points during the OGTT). Pairwise multiple comparison procedures were performed using the Holm-Sidak Method. Relations of interest were described using Pearson product-moment correlations. The level of statistical significance was set at $P<0.05$. Data are reported as mean and standard deviation, unless otherwise indicated. Calculations were performed using commercially available statistical software (SigmaStat 3.0, Systat Software Inc., San Jose, California, USA).

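### No planned analysis separates a direct drug effect from a weight-mediated one, so the title's claim of benefit independent of weight loss is not supported by the SAP

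*Combined protocol and SAP*

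**What the plan says.** The clinical research title reads "Dapagliflozin Promotes Favorable Health Benefits That Are Independent Of Weight Loss In Overweight/Obese Adults". The lay summary (Purpose, item 1(a)) says it is unclear whether the health "benefits are due to SGLT2 inhibition per se, or as a secondary effect of weight loss", and Background 3(a) repeats this and refers to benefits not mediated by weight loss.

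The operational statements are narrower. The lay summary goes on: "We wish to compare the health benefits of dietary counseling for weight loss with and without concomitant use of an SGLT2 inhibitor". The first listed aim, in item 1(b) and again at the end of Background 3(a), is whether the drug "provides additional health benefits to dietary counseling for weight loss". The second concerns satiety signals.

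In the Statistical Analysis Plan, "the influence of SGLT2 inhibition on the physiological responses to dietary counselling was examined using two-way" ANOVA, specified as "two-way (group: placebo vs. SGLT2 inhibition x time: before vs. after dietary counselling) analysis of variance (ANOVA"). The glucose tolerance data get a three-way ANOVA ("placebo vs. SGLT2 inhibition x before vs. after dietary counselling x time points during the OGTT"). The rest consists of baseline t-tests, Holm-Sidak pairwise comparisons and Pearson correlations for relations that are not named. No listed model contains weight or weight change, although weight is taken at the counselling visits and body composition is measured before and after treatment (Study Procedures, item 2(a)).

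**The concern.** Weight loss is itself an outcome of treatment. If the drug arm loses more weight, any outcome that follows weight, such as blood pressure, inflammation, oxidative stress or glucose handling, will tend to improve more in that arm even if the drug does nothing else. A significant group by time term is then a correct finding of added benefit, but it says nothing about the route. The title makes a claim about the route, and the plan contains no analysis on which to rest it. At stake is whether the report can honestly carry the wording of its own title.

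**Working it through.** **Sample size.** The target is 60 participants in two arms (Study Procedures, overview). The approval letter allows up to 200 enrolled so that 60 complete. No power, effect size or SD is given, so 60 cannot be reproduced. For orientation, with 30 per arm and two-sided 5%, the effect detectable with 80% power is (1.96 + 0.842) × √(2/30) = 0.72 SD.

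**What the test estimates.** With two time points and complete data, the group by time interaction is the same test as a two-sample t-test on change scores, with 58 degrees of freedom. It estimates the direct effect plus the weight-mediated effect.

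**Inputs assumed.** The documents do not give these: 30 per arm; two-sided 5%; within-arm correlation ρ between weight change and outcome change of 0.3, 0.5 or 0.7; extra weight loss on drug of w SDs of weight change; direct effect zero.

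**Formula.** The standardised total effect is d = ρ × w. The noncentrality is d × √(30/2) = 3.873 d, and the critical value is 2.00. Example: ρ = 0.5 and w = 1.0 give d = 0.50 and noncentrality 1.94, hence 48% significant.

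| Extra weight loss w | ρ = 0.3 | ρ = 0.5 | ρ = 0.7 |
|---|---|---|---|
| 0 | 5% | 5% | 5% |
| 0.25 SD | 6% | 8% | 10% |
| 0.5 SD | 9% | 16% | 27% |
| 1.0 SD | 21% | 48% | 76% |

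If the SD of weight change is taken as 2–4 kg (an assumption), a 1 kg difference between arms corresponds to 0.25–0.5 SD.

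**Can the test tell the routes apart?** Simulation, 10,000 trials per scenario, extra weight loss 1.5 SD:
- Effect wholly through weight (ρ = 0.5, total 0.75 SD): group by time significant in 81%; arm term adjusted for weight change, 5%.
- Effect wholly direct (0.75 SD, outcome unrelated to weight): group by time 82%; adjusted arm term 62%.

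The planned test behaves the same in both cases.

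**Do the correlations help?** If weight change were one of the unnamed relations, then at ρ = 0.5 the pooled Pearson correlation would be significant in 97–99.9% of trials whether the effect was mediated, direct or absent. It does not isolate a direct effect.

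**Is adjustment safe?** Only without an unmeasured common cause of weight change and outcome change. Suppose one explains half the variance of weight change and has a coefficient of 0.3–0.7 SD on the outcome, with no direct effect. The adjusted arm term is biased by coefficient × √0.5 × w. For 0.7 and w = 1.0 that is 0.7 × 0.707 × 1.0 = 0.49 SD. It is then significant in about 7–18% of trials at w = 0.5 and about 12–48% at w = 1.0.

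The direction depends on signs. A cause that increases weight loss and improves the outcome, as dietary adherence might, biases the adjusted term against the drug. One that increases weight loss but worsens the outcome biases it towards a false direct benefit.

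**The case against.** The strongest reply is that the trial's listed aims do not include independence from weight loss. The other protocol title, the comparison stated in the lay summary and the first aim all ask what the drug adds to counselling, and for that question the total effect is the right quantity. This stands, and the group by time contrast should stay. It does not cover the clinical research title or the question posed in the lay summary and Background.

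The second reply is that the arms may lose similar weight. Participants are steered to a target weight, with extra counselling after three consecutive weigh-ins outside 1 kg, and visit frequency in the second six weeks depends on progress. Background 3(a) also reports negligible weight loss with this drug class in adults with normal glucose control in the earlier study. Both could narrow the difference, and with equal loss the rejection rate falls to 5%. But the documents do not say how targets are set, do not require equal loss between arms, and do not plan to use weight loss in interpretation. The Risks section lists loss of up to 10 lb over 12 weeks with the drug.

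The third reply is that adjusting for a post-randomisation variable can mislead. That is correct, as the last step of the working shows. It is a reason to label the adjusted model exploratory and to restrict the claim.

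A reader might go further and infer that the two-way ANOVA is the only planned test, or that a weight-mediated effect will be reported as a direct one. The SAP lists several other analyses, and it describes its contrast only as the influence of the drug on responses to counselling. It states no direct-effect conclusion.

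**Conclusion.** The plan as written answers the first listed aim and leaves the title's independence claim without an analysis behind it. With no direct effect, the planned test is significant in 5% of trials at equal weight loss, rising to 21–76% at a 1.0 SD difference between arms. These figures rest on 30 per arm, two-sided 5% and correlations of 0.3–0.7, none of which the documents state. Where the trial falls in that range depends on a weight difference that cannot be predicted from the documents.

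It would be too strong to say that the trial can never address the question. The weight data are collected, so a weight-adjusted analysis is possible under a stated assumption; it is simply not planned.

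**What to change.** 1. State in the SAP that the group by time contrast estimates the total effect and does not by itself support independence from weight loss. Limit the conclusion to added benefit over counselling.
2. For each benefit outcome, add one model labelled exploratory: post-treatment value on arm, baseline value, baseline weight and weight change. Report the arm coefficient with its 95% CI beside the total effect and the between-arm difference in weight loss. State the assumption of no unmeasured common cause of weight change and outcome, naming dietary adherence as an example. Add a sensitivity analysis showing how strong such a cause would have to be to account for the arm coefficient. Because the SAP is written in the past tense, call the model post hoc if outcome data have already been seen.
3. Do not make an interval that excludes zero the rule for claiming independence. Describe such a result as consistent with a weight-independent effect under the stated assumption.

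The cost is SAP wording and one model per outcome on data already collected. The adjusted term can lose power when the arms differ in weight loss (62% against 82% in the direct-effect scenario above), and it relies on an assumption that the trial cannot test.
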